1.0 Study Summary

Study Title	A pilot study to evaluate single dose indocyanine green 24 hours prior to operative treatment of orthopaedic infection.	
Study Design	Prospective Observational Trial	
Primary Objective	The primary study objective is to explore the variability associated with bone and soft tissue perfusion in infection patients, using ICG fluorescence imaging.	
Secondary Objective(s)	The secondary study objective is to evaluate the change in single dose, 24h ICG distribution from pre to post debridement.	
Research Intervention(s)/ Investigational Agent(s)	Indocyanine green (ICG)-based dynamic contrast enhanced fluoresce imaging (diagnostic test)	
IND/IDE #	N/A	
Study Population	Patients 18 years of age or older who present to DHMC with an orthopaedic infection	
Sample Size	20 patients	
Study Duration for individual participants	6 months	
Study Specific	CDC: Centers for Disease Control and Prevention	
Abbreviations/	CRU: Clinical Research Unit	
Definitions	CRF: Case Report Forms	
	DCE-FI: Dynamic Contrast Enhanced Fluorescence Imaging D-HH HRPP: Dartmouth-Hitchcock Human Research	
	Protection Program	
	DHMC: Dartmouth Hitchcock Medical Center	
	GCP: Good Clinical Practice	
	GFR: glomerular filtration rate	
	ICG: Indocvanine Green	
	NSF: nephrogenic sclerosing fibrosis	
	ROI: Region of interest	
	SSI: Surgical Site Infection	

Page 3 of 21

Objectives*

The primary study objective is to explore the variability associated with bone and soft tissue perfusion in infection patients, using ICG fluorescence imaging.

The secondary study objective is to evaluate the change in single dose, 24h ICG distribution from pre to post debridement.

The third study objective is to preliminarily determine whether a single dose of ICG given 24h preoperatively can predict recurrent infection/treatment failure

2.0 Background*

The focus of this study is to (1) Explore variability in distribution of 24h ICG in bone and soft tissue infection (2) Evaluate the change in 24h ICG distribution from pre to post debridement (3) Preliminarily determine whether 24h ICG has the possibility predict infection / treatment failure

Infection following trauma is one of the most prevalent and challenging complications faced by orthopedic surgeons in both military and civilian populations, occurring after up to 60% of open bone fractures¹⁻⁷. Several factors specific to this trauma place patients at high risk for infectious complications, including: traumatized tissues, open contaminated fracture, soft tissue coverage issues, catabolic state due to poly-trauma, prolonged hospitalization with exposure to nosocomial bacteria, and presence of metallic implants⁸. Infection requires one or more unplanned surgical procedures and leads to prolonged morbidity, loss of function, and potential loss of limb^{1, 9-11}. Failed treatment for bone infection results in recurrent infection, requiring repeat surgical procedures in approximately 30% of patients.¹²⁻¹⁵

We are currently enrolling patients into a study to evaluate the utility of first window ICG to identify areas of deficient perfusion. This is based upon the concept deficient perfusion prevents delivery of antibiotics and endogenous immune cells to traumatized tissues. In the setting of established infection, poorly perfused bone can be a nidus for biofilm formation creating resistance to antibiotics. However, in the context of this work it is becoming increasingly clear that acute (rather than chronic) infections display hyper vascularity with increased blood flow and neovascularization. Infection is known to display the enhanced permeability and retention effect with increased vascular permeability. Second window or 24h ICG represents an ideal method to identify these areas of increased vascular permeability. In some instances infected tissue can be hard to distinguish from healthy

v.26Oct2022

Page 4 of 21

tissue when ICG is given immediately before optical imaging Second window ICG will allow surgeons to better distinguish infected tissue from healthy tissue as the ICG will have a better opportunity to permeate the infected tissue while it will have been expelled from the health tissue.

There are currently no accepted intraoperative tools that can be used to make objective decisions about which bone and tissue is infected and which is normal. Methods currently used to guide debridement are quite rudimentary. Clinical judgement is based on the gross appearance of soft tissue and bone, including color, turgor, and extent of soft tissue stripping. A burr may be used to look for bleeding bone. More extensive debridement is thought to minimize risk of index infection or reduce the rate of persistent infection; however, this comes at the cost of increasingly complex reconstructive procedures to fill bony defects²² ^{23, 24}. Clearly what is needed is a functional imaging system which can identify infected tissues to guide surgeons in the amount of tissue to debride. In turn, this will lead to fewer infections and a more effective treatment of SSIs at the fracture site. Both scenarios will allow patients to return to duty or work sooner.

3.0 Study Endpoints*

The study endpoint is to determine the variability of bone and soft tissue perfusion in infection patients when given a single dose of ICG 24h prior to surgical debridement. The long term goal of this study is to aid in the development and optimization of bone specific imaging strategies that can be used to guide debridement and to optimize the quality of bone / tissue resection to minimize complications.

4.0 Study Intervention/Investigational Agent

1. **Description:** This study is neither a drug nor a device trial. Patients will be administered FDA approved ICG through intravenous injection and imaged by either a FDA approved surgical fluorescence imaging device (Spy Elite) or the Zeiss Penero 800 both of which are held approximately 0.5 meter away from the subject. ICG fluorescence and both the Spy elite imaging system and the Zeiss Penero 800 surgical microscope have been used for routine clinical practice for many years. ICG fluorescence imaging utilizes intravenously injected ICG, which is a fluorescence idy that is FDA-approved for clinical use, illuminated with near-infrared light. The ICG dye is indirectly activated and the dynamic fluorescence due to bone perfusion can be captured by a video rate imaging system.

2. **Drug/Device Handling:** Indocyanine green (ICG) study medication will be ordered and stored by the investigational pharmacy for administration pre operatively.

ICG is FDA approved for routine clinical practice. No return or destruction of study drug is needed for this study.

3. Dose Rationale: We plan a sample size of 20 patients in this open label prospective observational study of ICG fluorescence imaging for patients with orthopaedic infection No randomization will be performed. For each patient enrolled in the study 2.5 - 5mg/kg ICG will be injected intravenously 24h prior to surgical debridement. Previous studies by [name] have indicated that the upper range of the dose may be necessary to obtain acceptable imaging (letter of support attached). ICG fluorescence images will be acquired pre and post-surgical debridement.

5.0 Procedures Involved*

Eligible patients regardless of ethnicity or health status, will be identified and recruited subject to inclusion and exclusion criteria above. Patients who meet eligibility criteria will be asked to participate in the trial. If they agree, written informed consent will be obtained from the patient or their healthcare proxy. To obtain informed consent, study personnel (surgeon or research coordinator) will adhere to the following procedures: (1) present study information in a manner that is understandable to the patient; (2) discuss the study with the patient and answer any questions; (3) allow the patient an opportunity to discuss participation with their family; (4) confirm that the patient understands the risks and benefits of participating in the study and that their participation is voluntary; (5) complete the consent process and obtain signatures from the patient and research team. The process of obtaining and documenting informed consent forms will be completed in accordance with local Good Clinical Practice (GCP) recommendations.

If the research team member obtaining consent is at all unsure about the patient's ability to consent, s/he will consult with the study PI.

This study seeks to include individuals with lacking or limited decision making capacity. A legally authorized representative (LAR) with reasonable knowledge of the potential participant will be approached to consent on the patient's behalf if the patient cannot adequately answer at least 2 questions about the study, or it is determined that the patient's level of cognition is not likely to change before study medication (ICG) can be administered. These questions will be to assess the participant's understanding of the study and

v.26Oct2022

Page 6 of 21

what it means to participate, their appreciation of the consequences of participation, and their ability to consider alternatives to participation.

The choice of LAR will follow standard procedures. The following with be approached in this order of priority:

- Legal guardian
- Proxy (health care agent) named in an advance directive or durable power of attorney for health care;
- Family member or other surrogate identified by the state law on health care decisions.

Guidance will be provided to assist the LAR in making the consent decision. They will advised to base the decision on the participant's expressed wishes, or, if these are not known, what they believe the participant would have desired under the circumstances of the injury, their beliefs and values. If the LAR does not know what the participant would have wanted, the LAR will advised to base the decision with the participant's best interest in mind. They will be asked to carefully consider how much leeway the participant would likely give the LAR in making the choice about participation in the study.

Recognizing that consent is an ongoing process, the study team will encourage the participants to ask additional questions that may arise during the course of their participation in the study.

If the patient is inpatient at the time of ICG administration then no additional IV access will need to be obtained. If the patient is dosed with ICG in the CRU then a qualified member of the CRU staff will insert the IV and then remove it before the patient leaves the CRU.

Patients will be administered a single, ICG, 2.5-5mg/kg dose 24 hours prior to surgery by a qualified member of their care team. The patient will be prepared and transported to surgery as per routine at Dartmouth-Hitchcock. In the OR, patient positioning, preparation of the surgical field, and draping will follow standard practice, of fracture fixation or joint fusion or requiring open surgical debridement/saucerization for osteomyelitis.

ICG fluorescence images will be acquired prior to surgical debridement. Debridement will then proceed per standard of care. The wound will be irrigated with a minimum of 3 liters irrigation with normal saline. After irrigation and debridement is completed another ICG fluorescence image will be acquired.

Costs associated with the purchase and administration of ICG will be billed directly to the study. Neither the patient or their health insurance provider will be responsible for any costs associated with the imaging procedures or the ICG administrations. The patient and / or their insurance company will be billed for a pregnancy test as part of routine surgery precautions for women of childbearing potential.

The need for repeat debridement or tissue cultures will be left up to the treating surgeon. If repeat debridement is needed, pre- and post-debridement quantitative ICG fluorescence images will be obtained at each procedure. In the situation where a debridement surgery is repeated on another date, the subject will undergo consent as outlined in the protocol for each additional surgery for which imaging will be obtained. If the skin wound is unable to be closed, it will be left open with a sterile dressing until delayed coverage in collaboration with plastic surgery.

ICG will be administered by a qualified member of the care team. During administration patients will either be under the care and observation of the inpatient care teams or closely monitored by a qualified member of the CRU for at least 30 minutes post ICG administration. Postoperatively, patients are transferred to the Post-Anesthesia Care Unit (PACU) where they are monitored continuously by nursing staff supervised by anesthesiologists. During this entire time vital signs (including temperature, pulse, respiratory rate and blood pressure) are collected as standard of care. All clinical data will be reviewed for adverse events for a period of 24 hours post-injection by members of the care team.

Day of Injection Procedures	Pre- Infusion	Up To 24 Hours Post Injection
Pulse	Х	Х
Blood Pressure	Х	Х
Temperature	Х	Х
Respiratory Rate	Х	Х
Adverse Events		Х

Upon admission and throughout the hospital course, patients will be treated with antibiotics per standard of care by the orthopaedic service or in collaboration with infectious disease recommendations. Management of study patients including clinical and radiographic assessments will not differ from standard of care.

Study participants will be followed for a period of 6 months following injection of 24h ICG. Final follow-up will be at 6 months to capture all infectious complications (Figure C.2)³⁵. If a participant does not return to clinic, follow-up may be conducted by telephone. SSI and unplanned fracture-related reoperations will be identified at the time of diagnosis/occurrence and/or during each participant clinical assessment and medical record review that will occur during their routine outpatient clinic visits. *Figure C.2 follow up assessments*

Assessment	Visit 1: Enrollment	Visit 2: 6 months
Eligibility Screening	•	
Informed Consent	•	
Collection of Demographic and Fracture/Infection Data	•	
Collection of Surgical Data	•	
Collection of Peri-Operative Data	•	
Collection of Outcome Data		•
Collection of Serious Adverse Events	•	•

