10.0 Vulnerable Populations*

In order to ensure that this study is not biased against patients with the most severe infections, who are most likely to benefit from this imaging device, patients who are cognitively impaired (most likely due to head trauma) will be eligible for this study.

A legally authorized representative (LAR) with reasonable knowledge of the potential participant will be approached to consent on the patient's behalf if the patient cannot adequately answer at least 2 questions about the study or it is determined that the patient's level of cognition is not likely to change before study medication (ICG) can be administered. These questions will be to assess the participant's understanding of the study and what it means to participate, their appreciation of the consequences of participation, and their ability to consider alternatives to participation.

The choice of LAR will follow standard procedures. The following with be approached in this order of priority:

- Legal guardian
- Proxy (health care agent) named in an advance directive or durable power of attorney for health care;
- Family member or other surrogate identified by the state law on health care decisions.

Guidance will be provided to assist the LAR in making the consent decision. They will advised to base the decision on the participant's expressed wishes, or, if these are not known, what they believe the participant would have desired under the circumstances of the injury, their beliefs and values. If the LAR does not know what the participant would have wanted, the LAR will advised to base the decision with the participant's best interest in mind. They will be asked to carefully consider how much leeway the participant would likely give the LAR in making the choice about participation in the study.

This is in compliance with Checklist HRP-417 (Cognitively Impaired Adults). **11.0 Local Number of Subjects**

This is a pilot study to investigate the feasibility of obtaining fluorescence imaging following injection of ICG 24 hours prior to surgery for infection. This study seeks to enroll 20 patients. Several studies by this investigator inject ICG during surgery, however none have investigated ICG injection prior to surgery. The data collected in this pilot study will inform future studies involving ICG injection and the optimal time of injection.

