The risks to subjects are minimal in relation to anticipated benefits and/or knowledge that might reasonably be expected from the results of this clinical trial. ICG is FDA approved for human use in angiography for ophthalmology and cardiology applications and is given routinely to patients in these clinical settings. The risks are considered minimal and consist of nausea, vomiting, hives, increased heart rate in subjects with particular sensitivity to the dye. ICG does contain sodium iodide and patients with a history of allergy to iodides will be excluded. The ICG will be administered thru IV which the patient will have regardless of if they participate in this trial or not. There will be no additional study specific IV's placed.

ICG, the Spy Elite® imaging system and the Zeiss Pentero 800 surgical microscope are FDA approved for use in human subjects. Currently we are enrolling patients into a study to evaluate the utility of first window ICG to identify areas of deficient perfusion. This study seeks to evaluate ICG utility as a second window in areas of deficient perfusion. This study is to be conducted according to US and international standards of Good Clinical Practice (FDA Title 21 part 312 and International Conference on Harmonization guidelines), applicable government regulations and Institutional research policies and procedures.

Page 18 of 21

Patients with impaired decision-making capacity will be included in this study. If the patient is unable to provide informed consent (e.g. due to their injury) at the time they are identified, informed consent may be obtained from their legally authorized representative (LAR). Allowing informed consent from a patient's LAR will reduce the risk of recruitment bias against the most severely infected patients.

For patient with impaired decision-making capacity, a LAR with knowledge of the potential participant will be approached to consent on the patient's behalf. If the patient cannot adequately answer at least two questions about the study or it is determined that the patient's level of cognition is not likely to change before study medication (ICG) can be administered, their LAR will be approached.. These questions will be to assess the participant's understanding of the study and what it means to participate, their appreciation of the consequences of participation, and their ability to consider alternatives to participation.

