The choice of LAR will follow standard procedures. The following will be approached in this order of priority:

- Legal guardian
- proxy (health care agent) named in an advanced directive or durable power of attorney for health- care
- Family member or other surrogate identified by state law on health care decisions.

The LAR will be advised to base the decision on the participant's expressed wishes, or, if these are not known, what they believe the participant would have desired under the circumstances of the injury, their beliefs and values. Recognizing that consent is an ongoing process, the study team will encourage the participants to ask additional questions that may arise during the course of their participation in the study.

Subjects participation in this study completely voluntary. If at any time a patient finds participation to be unduly stressful the patient or their legal authorized representative may withdraw the patient from the study with no repercussions.

Assent will not be requested from subjects unable to consent for themselves.

The study team will comply with consent procedures for cognitively impaired adults outlined in SOP HRP-013.

This study will not recruit non-English speaking subjects.

This study will not involve the subjects who is under age 18.

Page 19 of 21

No other vulnerable patient populations not outlined by this protocol will be included in this study.

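### The surrogate-consent rule joins its two conditions with 'or', so a patient with impaired capacity who is expected to recover before the ICG injection can be enrolled and dosed on a surrogate's consent

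*Protocol*

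**What the plan says.** The protocol deliberately includes patients with impaired decision-making capacity, and section 10.0 expects head trauma to be the usual cause. The rule for turning to an LAR appears three times:

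- Section 5.0: the LAR is approached "if the patient cannot adequately answer at least 2 questions about the study, or it is determined that the". The condition after the 'or' is a forecast about the same patient, namely that the "level of cognition is not likely to change before study medication (ICG) can be administered".
- Section 10.0: the LAR is approached if the patient "cannot adequately answer at least 2 questions about the study or it is determined that the" same expectation about cognition holds.
- Section 21.0, on cognitively impaired adults: again if the patient "cannot adequately answer at least two questions about the study or it is determined that the" same expectation holds. The paragraph before it sets the time at which inability is judged: "If the patient is unable to provide informed consent (e.g. due to their injury) at the time they are identified".

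Section 21.0 adds: "Assent will not be requested from subjects unable to consent for themselves". On continuing consent, section 5.0 says: "Recognizing that consent is an ongoing process, the study team will encourage the participants to ask additional questions". Section 15.0 states that participants gain no direct benefit.

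**The concern.** The condition about cognition before ICG has an obvious purpose: if the patient is likely to regain capacity before the injection, wait and ask the patient. That purpose is met only if it is an added requirement, so that surrogate consent needs both a failed capacity check and no expected recovery in time. Written with 'or', it is an alternative route to the LAR and holds nobody back.

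At stake is who decides on a research-only intravenous injection that cannot be undone. Section 14.0 describes the risk as minimal, with severe reactions at 0.05%, but it also notes that anaphylactic deaths have been reported. A patient who could have decided by the time of injection may first be able to refuse only after exposure.

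**Working it through.** No arithmetic applies; the check is of the rule's logic and of what follows it.

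**Inputs.** Let A = the patient fails the questions, and B = cognition is judged unlikely to change before ICG. Sections 5.0, 10.0 and 21.0 all state A or B. The rule applies to patients with impaired capacity, so the comparison is among those who fail the questions (A true):

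- A true, B true (incapable, no recovery expected): the LAR is approached under 'or' and under 'and'.
- A true, B false (incapable now, recovery expected before injection): the LAR is approached under 'or', but not under 'and'.

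Once A is true, B makes no difference under the written rule. The second line is the defect.

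**Can that case arise?** Yes. Section 21.0 judges inability when the patient is identified, while condition B looks ahead to the injection. The protocol thus treats these as separate times and recognises that cognition may change between them.

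**Does a later step catch it?** Going through the protocol in order:

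- Section 5.0, day-of-injection table: vital signs and adverse events only; no capacity check.
- Section 5.0, follow-up table: informed consent at enrolment only; none at 6 months.
- Sections 5.0 and 21.0, PI consultation: applies when the person taking consent is unsure of the patient's ability. It requires neither waiting nor asking again.
- Section 5.0, fresh consent for each additional imaged surgery: comes after the first injection and uses the same rule.
- Sections 5.0 and 21.0, consent as an ongoing process: leads only to encouraging questions.
- Section 21.0, withdrawal: open to patient and LAR, but it depends on one of them raising it.
- Section 21.0, assent: not sought from those unable to consent.

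None of these requires a recheck before the first injection, or requires the patient's own consent when capacity returns.

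**The case against.** The strongest reply is that the controlling procedure lies elsewhere. Section 21.0 binds the team to SOP HRP-013 for cognitively impaired adults, and section 10.0 cites Checklist HRP-417. Either may require reassessment and re-consent. This stands as a limit: one can say only that the protocol text is silent on rechecking. It does not rescue the trigger, which is written out three times and points the other way.

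A second reply is that section 21.0 says LAR consent may be obtained, which leaves room to wait. That is true of that sentence, but the next paragraph, like sections 5.0 and 10.0, says the LAR will be approached.

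A third is that the second condition may be meant for patients who cannot be questioned at all, such as the unconscious. They cannot answer adequately either, so they already meet the first condition and would still enter through the LAR under 'and'.

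Three stronger readings are tempting, and the protocol does not support them:

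- A reader might infer that a capable patient with stable cognition is also sent to an LAR, since the second condition alone would be met. The context excludes this: section 5.0 introduces the rule for people lacking or limited in decision-making capacity, section 10.0 for the cognitively impaired, and section 21.0 for impaired capacity.
- A reader might infer that assent is barred for a patient who has recovered. The exclusion covers only those unable to consent for themselves. It does not forbid asking a recovered patient; the gap is that nothing requires it.
- A reader might infer that each late refusal costs 1/20 = 5% of the outcome data. Section 13.0 keeps data already collected when a subject withdraws after imaging, and asks whether routine records may still be used for follow-up. Seeking own consent could also produce refusals that the present text would not, so data loss cannot be counted as a harm of the present rule.

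**Conclusion.** The point holds. As written in three sections, the rule allows a patient with impaired capacity who fails the questions at identification, but is expected to regain capacity before injection, to be enrolled and dosed on surrogate consent. The protocol text has no compulsory step at which that patient's own decision is sought before the first injection, or once capacity returns.

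Its size cannot be expressed as a count. The protocol gives neither the expected number of LAR consents nor how many such patients would recover between identification and injection. No endpoint, sample size or other statistical figure is affected. The matter is valid consent and participant protection, and it should be corrected because the stated rule defeats its own evident purpose. The conclusion assumes that the second condition was meant to limit surrogate consent, and that SOP HRP-013 and Checklist HRP-417, which are not shown, do not already override the protocol wording. If they do, the protocol should be brought into line with them.

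**What to change.** In sections 5.0, 10.0 and 21.0, replace 'or' with 'and', so that the LAR is approached only when the patient fails the questions and capacity is not expected to return before ICG. For every LAR-consented patient, repeat the existing questions before injection; if the patient passes, seek the patient's own consent before proceeding. If capacity returns during the 6 months of follow-up, seek the patient's own consent then and record the date. Check the wording against SOP HRP-013 and cite it at the trigger.

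The cost is one word in three sections, two added sentences, a few minutes of staff time per LAR-consented patient, and an occasional refusal that surrogate consent would not have produced. The protocol's stated reason for surrogate consent, avoiding bias against the most severely infected, is largely preserved: patients who remain incapable still enter through the LAR, and those who recover can enter on their own consent.

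### Adverse-event review ends 24 h after an injection given nominally 24 h before surgery or debridement, so non-serious events at the second image and in PACU fall outside it; separately, CRU-dosed patients have no specified contact before arriving for surgery

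*Protocol*

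**What the plan says.** **End of review.** Section 5.0 states: "All clinical data will be reviewed for adverse events for a period of 24 hours post-injection by members of the care team". The injection-day table in the same section agrees: adverse events and vital signs are marked in a column that runs to 24 hours after injection, and nowhere later.

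**Dose timing.** Section 5.0 counts back from surgery: "Patients will be administered a single, ICG, 2.5-5mg/kg dose 24 hours prior to surgery". The dose rationale in section 4.0 counts back from debridement: "ICG will be injected intravenously 24h prior to surgical debridement". Neither gives a tolerance.

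**What follows the anchor.** Section 5.0 continues: "After irrigation and debridement is completed another ICG fluorescence image will be acquired". Two sentences before the 24-hour limit it says: "Postoperatively, patients are transferred to the Post-Anesthesia Care Unit (PACU) where they are monitored continuously by nursing staff supervised by anesthesiologists".

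**Observation.** Section 14.0 has research, surgical and anesthesia staff watching for reactions to the dye whenever imaging is under way, and standard-of-care monitoring for the whole hospital stay.

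**Other collection.** The follow-up table in section 5.0 lists "Collection of Serious Adverse Events" at enrollment and at 6 months. It also lists surgical and peri-operative data at enrollment.

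**CRU-dosed patients.** Staff "insert the IV and then remove it before the patient leaves the CRU", and the patient is "closely monitored by a qualified member of the CRU for at least 30 minutes post ICG administration". No call, visit or question is specified between that point and arrival for surgery.

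**The concern.** The review window starts at injection, but the study procedures that follow are set about 24 h later. If both timings are kept as written, the review closes when the patient reaches surgery or debridement. Staff are then told to watch for dye reactions at the second image, yet a non-serious reaction seen there has no stated place in the adverse-event review. The same holds for PACU and for the operating time added by the second image. Section 14.0 puts the added operating time at no more than 10 minutes for the average case.

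The CRU gap is of a different kind. The interval is inside the window, but a review of clinical data has little to review for a patient who has left the unit and whom nobody is asked to contact.

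At stake is the completeness of the tolerability record. Section 11.0 says that none of this investigator's other studies has examined injection before surgery, and that the pilot data will inform later ones. Because actual intervals will vary around 24 h, similar non-serious events could also be recorded for one patient and not for another.

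**Working it through.** The protocol gives no figure to reproduce here, so the check compares time windows and then sizes the consequence.

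**Inputs from the protocol**
- Review window: 0 to 24 h after injection (section 5.0, text and table).
- Injection to anchor: 24 h nominal; the anchor is surgery (section 5.0) or debridement (section 4.0).
- Second image: after irrigation and debridement; then PACU (section 5.0).
- CRU observation: at least 30 minutes (sections 5.0 and 14.0).
- Reaction rates: 0.15% mild, 0.2% moderate, 0.05% severe (section 14.0).
- Sample size: 20 (section 11.0).

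**Step 1: nominal timing.** Let x be the actual time from injection to the anchor and t the time from the anchor to an event. The event is inside the review only if x + t ≤ 24 h. With x = 24 h this requires t ≤ 0. The second image and PACU both have t > 0, so they are outside on either anchor, however long surgery takes.

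**Step 2: how short the interval must be to close the gap.** The protocol gives no surgical or PACU times, so these are assumed.
- Second image at t = 1 to 3 h: inside only if x ≤ 24 − 1 = 23 h to 24 − 3 = 21 h.
- PACU discharge at t = 2 to 5 h: all of PACU is inside only if x ≤ 24 − 2 = 22 h to 24 − 5 = 19 h.

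So the gap depends on actual timing, and dosing some hours late relative to the nominal 24 h would close part or all of it. No section plans for that.

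**Step 3: CRU-dosed patients.** What the text assures inside the 24 h is:
- at least 30 minutes after dosing;
- on the surgery anchor, routine preparation and transport;
- on the debridement anchor, also positioning, draping and the first image, which section 14.0 requires to be monitored.

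Between leaving the CRU and arriving for surgery nothing is specified, although the table marks vital signs and adverse events up to 24 h and makes no exception for these patients. The length of that interval cannot be computed, because arrival time is not given.

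**Step 4: size.** These figures assume that the section 14.0 rates apply at this study's dose.
- All reactions: 0.15% + 0.2% + 0.05% = 0.4%; 20 × 0.004 = 0.08 expected.
- Chance of at least one: 1 − 0.996^20 = 7.7%.
- Mild or moderate: 20 × (0.0015 + 0.002) = 0.07 expected.

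The rates cover reactions at any time, so 0.07 is an upper bound on the expected number of mild or moderate dye reactions missed through both gaps together. They do not cover non-serious events caused by surgery or anesthesia.

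**The case against.** The strongest reply is that the window follows the exposure. There is one injection, no dye is given at the second image, and section 2.0 expects healthy tissue to have cleared the dye by then. A review tied to the injection is a defensible choice, and extending it will mainly bring in surgical events. This stands as a reason to expect few late dye reactions. It does not explain why section 14.0 has research staff watching for such reactions at the second image while section 5.0 gives no matching place to record a non-serious one.

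Three further replies stand in part:
- Peri-operative data are collected and the case report forms (CRFs) are not shown. They may capture some events, but the protocol does not say that these data include adverse events.
- Section 14.0 describes taking a history of allergies and sensitivities on arrival. It does not say which arrival, does not ask about events since injection, and does not make the answer an adverse-event record.
- The 24 h is nominal, so some patients may be covered through PACU. That depends on actual intervals that the plan does not fix.

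A reader might infer more than the text supports:
- *Patients are unmonitored after 24 h.* They are not: section 14.0 keeps bedside monitoring going during imaging and throughout the hospital stay.
- *The sections contradict one another on when review ends.* They do not: only section 5.0 states an end, and its text and table agree.
- *Half an hour in 24 is all the observation a CRU-dosed patient gets.* Thirty minutes is a minimum, and pre-operative care, plus the first image on the debridement anchor, also falls inside the window.

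**Conclusion.** The point holds as a minor one. At nominal timing the stated adverse-event review ends as surgery or debridement begins, so non-serious events at the second image, in the operating time it adds, and in PACU are outside it. CRU-dosed patients also have an interval inside the window with no specified contact. Both are gaps in recording, not in bedside care.

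The first conclusion rests only on the nominal 24 h. How far a shorter interval closes the gap rests on assumed surgical and PACU times. The expected count of 0.08 dye reactions in 20 patients rests on the section 14.0 rates applying at this dose. Safety is not a stated objective or endpoint, serious events are still collected to 6 months, and no study objective is affected. An unseen analysis plan would not remove the point, because the protocol itself sets the window.

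**What to change.** 1. In the section 5.0 text and injection-day table, run adverse-event recording from injection through PACU discharge after the imaged surgery. Recording then matches the observation already described in sections 5.0 and 14.0.
2. At surgical admission, ask CRU-dosed patients about events since injection and enter the answer on the CRF.
3. Report events before and after the start of surgery separately, so that surgical events are not mixed with possible dye reactions.

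These changes affect recording only; dose and clinical management are untouched. The cost is protocol and CRF wording plus one question at admission for CRU-dosed patients. Post-operative vital signs are already collected as standard of care. The downside is more surgery-related events to classify.
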